## **STUDY TIMELINES**

- One (1) screening visit
- One (1) Baseline assessment visit prior to initiating each arm (3 total)
- Fifteen (15) treatment/intervention visits, 5 per each intervention arms
  - The treatment sessions will be up to 5 times per week within each participants' scheduling availability
- One (1) Functional Assessment visit that occurs after all intervention sessions are complete for each arm (POST, 3 total)
- One (1) Functional Assessment visit that occurs 1 week after all intervention sessions are complete for each arm (1 week follow up, 3 total)

We anticipate an ongoing enrollment over 3 years. Investigators will complete this study (primary analyses) 5 years from start date (IRB approval date).

## **INCLUSION AND EXCLUSION CRITERIA**

### **Inclusion Criteria:**

- Participants have been diagnosed with a spinal cord injury below level C2
- ASIA Impairment Scale Grade A-D
- Participants are 18 years of age or older
- Participants are at least 6 months post spinal cord injury
- Participants with paraplegia or tetraplegia secondary to a single spinal cord injury
- Participants are able to provide informed consent
- Participants are not currently receiving regular physical therapy services

### **Exclusion Criteria**

- Individuals less than 18 years of age
- Individuals less than 6 months post spinal cord injury
- Individuals with cerebellar ataxia
- Individuals with multiple spinal cord injury history
- Pregnancy or nursing
- Pacemaker or anti-spasticity implantable pumps
- Active pressure sores
- Unhealed bone fractures
- Peripheral neuropathies
- Painful musculoskeletal dysfunction due to active injuries or infections

- Severe contractures in the lower extremities
- Active urinary tract infection
- Clinically significant depression, psychiatric disorders, or ongoing drug abuse
- Diagnosed with any of the following medical conditions: congestive heart failure, cardiac arrhythmias, uncontrolled hypertension, uncontrolled diabetes mellitus, chronic obstructive pulmonary disease, emphysema, severe asthma, previous myocardial infarction, or known carotid/intracerebral artery stenosis
- Individuals with a tracheostomy or who utilize mechanical ventilation.
- Individuals who are currently enrolled in another interventional research study or in therapy related to lower extremity function and/or walking.
- Participants will be excluded if they have had a botulinum toxin injection to lower extremity musculature within the last 3 months. Participants will need to refrain from lower extremity botulinum toxin injections for the duration of the study. If participants wean off antispasticity medications to successfully complete the responsiveness to AIH screening session, they will need to refrain from the medications for the duration of the study.
- Documented sleep apnea.
- Orthopedic injuries or surgeries that would impact an individual's ability to use the lower extremity.
- Traumatic brain injury or other neurological conditions that would impact the study.

We will not include the following populations:

- Adults unable to consent, unless accompanied by a legally authorized representative.
- Individuals who are not yet adults (infants, children, teenagers)
- Pregnant women
- Prisoners

#### PARTICIPANT POPULATION(S)

Accrual Number:	Category/Group: (Adults/Children Special/Vulnerable Populations)	Consented: Maximum Number to be Consented or Reviewed/Collected/Screened	Enrolled: Number to Complete the Study or Needed to Address the Research Question
Local	Adults	45	36
Study-wide	Single-Center Study	0	0
Total:		45	36

#### STATISTICAL ANALYSIS PLAN:

All functional gait outcomes will be assessed at three follow-up visits. We will use a linear mixed model with repeated measures to jointly assess changes at INT5, POST and 1WK relative to baseline within each arm as well as assess the changes between arms for each time point. The model will include time points (BL, INT5, POST, and 1WK as a categorical variable) and treatment arm (AIH + tSCS, SHAM AIH + tSCS, and SHAM + SHAM as categorical variable) as fixed effects and subject as a random effect. Linear mixed models provide a better mechanism for handling missing data by using all available data, rather than performing a complete case

analysis, if the data are assumed to be missing at random. The level of significance will be set at alpha = 0.05. Bonferroni corrections will be used to adjust for multiple comparisons.

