**OBJECTIVES:**

- To determine whether acute intermittent hypoxia therapy (AIH) combined with transcutaneous electrical spinal cord stimulation during ambulation training modulates spinal locomotor networks in individuals with spinal cord injury

- To determine whether acute intermittent hypoxia therapy (AIH) combined with transcutaneous spinal cord stimulation during ambulation training improves locomotor function in individuals with spinal cord injury
- To determine whether ambulation efficiency (improved cardiovascular conditioning) improves with training combination of AIH, transcutaneous spinal cord stimulation and ambulation training in individuals with spinal cord injury

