### **Treatment Sessions**

Each participant will complete 5 treatment sessions in each of the 3 arms of the study. Treatment sessions will take place 5 times per week.

Each treatment session may include:

- *Arm 1: AIH + tSCS*
  - May receive up to 45 minutes of AIH and 30 min of locomotion training with transcutaneous spinal cord stimulation.
- *Arm 2: SHAM + SHAM*
  - May receive up to 45 minutes of sham AIH and 30 min of locomotion training with sham transcutaneous spinal cord stimulation.
- *Arm 3: SHAM AIH + tSCS*
  - May receive up to 45 minutes of sham AIH and 30 min of locomotion training with transcutaneous spinal cord stimulation.

Under all of the conditions, the goal during locomotor training is to generate smooth and symmetrical stepping movements. The trained research personnel will provide cues (verbal, visual and tactile) to improve symmetry of gait and avoid compensatory mechanisms. The progression in training refers to gradually increasing gait speed while maintaining improved gait kinematics. Electromyographic (EMG) activity will be collected from the lower extremity muscles bilaterally during maximum voluntary contractions and locomotor training.

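### The SAP tests change from baseline within each arm beside the between-arm contrasts and does not say which decides efficacy, so a gain from training shared by all arms could be reported as an AIH + tSCS effect

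*Combined protocol and SAP*

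**What the plan says.** The Statistical Analysis Plan section gives the linear mixed model two jobs in one sentence. The first is to "jointly assess changes at INT5, POST and 1WK relative to baseline within each arm". The arm comparison follows as the second job, worded "as well as assess the changes between arms for each time point". Neither is called primary, confirmatory or descriptive. On the model it says: "The model will include time points (BL, INT5, POST, and 1WK as a categorical variable) and treatment arm", and these enter "as fixed effects and subject as a random effect". No arm-by-time interaction is listed. On error control it says "The level of significance will be set at alpha = 0.05" and "Bonferroni corrections will be used to adjust for multiple comparisons", without defining the family of comparisons.

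Other sections do not settle which test decides:

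- The Objectives ask whether AIH "combined with transcutaneous spinal cord stimulation during ambulation training improves locomotor function".
- The Study Endpoints section defines the primary endpoint as a change in the 6MWT and names no arm contrast.
- Under Treatment Sessions every arm trains walking. Even the double-sham arm receives "30 min of locomotion training with sham transcutaneous spinal cord stimulation", and training progresses by raising gait speed.
- The Sample Size and Power Considerations section uses a one-sided paired t-test on 10MWT speed from before treatment to one week after, with a target of 0.06 m/s and an SD of 0.07 m/s for change from baseline. It names no comparator arm.

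**The concern.** A change from baseline in the AIH + tSCS arm combines any effect of AIH and stimulation with the effects of the training itself, repeated walking tests and attention. The sham arms exist to remove those shared components, and only the between-arm difference in change does so. The within-arm null hypothesis is false whenever training helps at all, so rejecting it says nothing about AIH or stimulation. A multiplicity correction cannot repair that, because these rejections are correct answers to a different question.

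If the plan does not say which test decides, the choice can be made after the results are seen. A report could then state that walking improved significantly with the combination although the arms did not differ. It could also set a significant result in one arm against a non-significant result in another, which is not a test of the difference between them.

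**Working it through.** **Inputs.** SD of change 0.07 m/s, target 0.06 m/s and alpha 0.05 (Sample Size and Power Considerations); n = 36 (Study Summary). The documents give no size for a shared gain g, so g = 0.02, 0.03 and 0.06 m/s are assumed. They also give no within-person correlation rho between a participant's changes in two arms, so 0 to 0.75 is shown. The illustration uses 10MWT speed because the documents give no SD for the 6MWT. Simple t-tests stand in for the mixed-model contrasts, with complete data.

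**1. The plan's own figure.** Effect size 0.06/0.07 = 0.857. Power comes from the noncentral t with n − 1 degrees of freedom and noncentrality 0.857 × √n. One-sided at 0.05, n = 10 gives 80.3% and n = 9 gives 75.8%. The stated n = 10 for 80% is reproduced.

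**2. Within-arm test when no arm effect exists.** Noncentrality is (g/0.07) × √36 with 35 degrees of freedom, two-sided. The SAP does not define its Bonferroni family. If all planned tests for one outcome are counted, there are 3 arms × 3 times = 9 within-arm tests and 3 arm pairs × 3 times = 9 between-arm tests, so 18 in all.

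| Shared gain (m/s) | Noncentrality | Significant at 0.05 | Significant at 0.05/18 |
|---|---|---|---|
| 0.02 | 1.71 | 38.5% | 8.3% |
| 0.03 | 2.57 | 70.6% | 28.0% |
| 0.06 | 5.14 | 99.9% | 96.5% |

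**3. Between-arm test in the same setting.** The difference between two arms' changes has mean g − g = 0, so the shared gain cancels. In simulation (gains 0.03 and 0.06, rho = 0.5, 20,000 runs) this test rejected in 4.8% to 5.2% of trials.

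**4. Significant with AIH + tSCS but not with SHAM + SHAM.** At a gain of 0.03 and alpha 0.05, independent arms give p(1 − p) = 0.706 × 0.294 = 0.208, or 21%. Each participant completes all arms, so changes may correlate. Simulation gives about 18%, 14% and 10% at rho = 0.25, 0.5 and 0.75. At a gain of 0.06 and alpha 0.05 the pattern almost vanishes (about 0.1%), because both arms are nearly always significant; at 0.05/18 it is about 2% to 3%.

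**5. What the listed model can estimate.** With arm and time as main effects only, the mean is μ + arm + time. Change from baseline is then the time effect alone, identical in every arm, and the between-arm difference in change is zero by construction. Neither quantity that the SAP wants can be obtained without an arm-by-time interaction.

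**6. Can the trial rely on the between-arm contrast?** Its SD is 0.07 × √(2(1 − rho)). For a 0.06 m/s arm difference and 80% power, two-sided:

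| rho | SD (m/s) | n at 0.05 | n at 0.05/3 | n at 0.05/9 |
|---|---|---|---|---|
| 0 | 0.099 | 24 | 32 | 40 |
| 0.25 | 0.086 | 19 | 25 | 31 |
| 0.5 | 0.070 | 13 | 18 | 22 |
| 0.75 | 0.049 | 8 | 11 | 13 |

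The planned 36 is enough in every cell except nine contrasts with rho = 0.

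**The case against.** The trial is randomised and sham-controlled, and the SAP already plans the comparison that removes a shared gain. A reader might infer that a common training gain would be declared an effect of AIH + tSCS. The documents do not support that, because they contain no rule that counts a within-arm change as efficacy. Nor does naming the within-arm changes first rank them above the arm comparisons. Both objections stand and limit the point to what could happen.

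A reader might also take the sample size as proof that the trial is designed around a pre-post change. The wording is open: in a crossover, a paired test on changes can mean one arm's change against another's, and an SD of 0.07 m/s fits that reading if rho = 0.5. The missing comparator and an SD described as change from baseline favour the pre-post reading but do not settle it.

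The numbers depend on an assumed gain. At 0.06 m/s, five sham sessions would have to deliver the whole target difference, so that row is an upper end. The 21% in step 4 requires uncorrelated arms, which is the high end of the range shown, and the plan nowhere proposes to infer an arm difference from such a pattern. The illustration also concerns a secondary endpoint. None of this changes the direction: any shared gain raises the within-arm rejection rate and leaves the between-arm rate alone.

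**Conclusion.** The point holds in a limited form. The SAP plans significance tests that cannot answer the objective, gives them no lower standing than those that can, and names no deciding contrast anywhere. With 36 participants, an SD of 0.07 m/s in each arm and no true arm difference, a modest shared gain of 0.03 m/s makes the AIH + tSCS within-arm test significant in about seven trials in ten at 0.05, and in more than one in four at 0.05/18. The contrast between a significant active arm and a non-significant sham arm arises in about 10% to 21% of trials at that gain and 0.05, depending on rho. The size rests on the assumed gain; the conclusion that only the between-arm difference isolates AIH and stimulation does not. This should be corrected before analysis. It does not undermine the design, which already supplies the valid comparison.

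**What to change.** In the Statistical Analysis Plan section:

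1. State that efficacy conclusions rest only on between-arm differences in change from baseline.
2. Add the arm-by-time interaction to the listed fixed effects and say that these differences are estimated from it.
3. Report within-arm changes descriptively, as estimates with 95% confidence intervals and no significance claims.
4. Define the Bonferroni family as the between-arm contrasts only. By the count above this cuts it from 18 to 9 comparisons per outcome, and naming fewer arm pairs or time points would cut it further.

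The Sample Size and Power Considerations section should then say whether its 0.06 and 0.07 m/s refer to a difference between arms and, if so, what within-person correlation is assumed.

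The cost is a few sentences and one model term, with no extra participants or visits. What is given up is the ability to claim significance for change within an arm.

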### **PROCEDURES INVOLVED:**

Study Design: A randomized, controlled crossover trial. We are evaluating the effectiveness of AIH prior to transcutaneous spinal cord stimulation during locomotor training on improving ambulation and standing balance among individuals with paraplegia or tetraplegia due to spinal cord injury. All participants will complete three arms of the study:

1. AIH prior to transcutaneous spinal cord stimulation during locomotor training (AIH + tSCS)
2. Sham AIH prior to sham transcutaneous spinal cord stimulation during locomotor training (SHAM + SHAM)
3. Sham AIH prior to transcutaneous spinal cord stimulation during locomotor training (SHAM AIH + tSCS)

Participants will complete a 4-week washout period between each arm.

Prior to Visit 2, a medical clearance letter describing study procedures and risks will be sent to the subject's physician or clinician to request medical clearance for the subject to participate in the study. Permission to contact the participant's physician or clinician to obtain medical clearance will be obtained during the screening process.

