**SAMPLE SIZE AND POWER CONSIDERATIONS:**

The sample size calculation will be based on a one-sided paired *t*-test comparing the changes in self-selected speed of the 10 meter walk test from pre- to 1 week post-treatment. Based on the minimum clinically important difference (MCID) for speed previously reported in SCI29, we want to detect a change in speed of 0.06 m/s. The standard deviation of the change from baseline to 1 week post was 0.07 m/s. Therefore, using 0.857 as our effect size, a sample size of n=10 will provide a power of 80% with alpha = 0.05.

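### Comparing arms on change from each period's baseline, rather than adjusting for those baselines, gives away precision in this crossover: between 10% and 50% of the contrast variance over a plausible range

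*Combined protocol and SAP*

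**What the plan says.** The design is a three-arm crossover (Procedures Involved): "All participants will complete three arms of the study", and "Participants will complete a 4-week washout period between each arm". Study Timelines schedules "One (1) Baseline assessment visit prior to initiating each arm (3 total"), so each participant contributes three baselines.

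The Statistical Analysis Plan section aims to "assess changes at INT5, POST and 1WK relative to baseline within each arm as well as assess the changes between arms", taking each time point in turn. On the model it says: "The model will include time points (BL, INT5, POST, and 1WK as a categorical variable) and treatment arm", these entering "as fixed effects and subject as a random effect". Baseline is therefore part of the response. The section names no baseline covariate, no constraint on the baseline means, no arm-by-time interaction, no period effect and no participant-by-period effect. On multiplicity it says only: "Bonferroni corrections will be used to adjust for multiple comparisons".

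The sample size section is also framed on change: "The sample size calculation will be based on a one-sided paired *t*-test comparing the changes in self-selected speed of the 10 meter walk test", from before treatment to 1 week after.

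**The concern.** A crossover already removes stable differences between people, because each participant is compared with themselves. Subtracting a fresh baseline in each period is not needed for that purpose, and it has a price: a between-arm difference in changes carries the visit-to-visit error of two follow-ups and two baselines.

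Having baseline in the model as a response level does not avoid this. If each arm has its own free baseline mean, the arm-by-time contrast is a difference of change scores, which fixes the slope on baseline at 1. Baseline adjustment estimates that slope from the data.

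At stake is precision on the main between-arm questions, in a trial of 36 people with a Bonferroni correction over an unstated number of comparisons. The data needed to recover it are already being collected.

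**Working it through.** **Inputs from the documents.** Effect 0.06 m/s, SD of change 0.07 m/s, one-sided alpha 0.05, n=10 for 80% power (sample size section); 36 participants (Study Summary and the accrual table).

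**The plan's own figure.** The effect size is 0.06/0.07 = 0.857. A one-sided paired t-test with n=10 has power 0.803 (noncentral t, 9 df), and 10 is the smallest n that reaches 80%. The stated figure reproduces.

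**Variance of the two contrasts.** Let s² be the within-person variance of one visit, equal at baseline and follow-up. Let r be the baseline/follow-up correlation within a period after the participant effect is removed, with periods otherwise independent. Per participant:

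- difference of changes: 2 arms × 2s²(1−r) = 4s²(1−r)
- baseline-adjusted difference: 2 arms × s²(1−r²) = 2s²(1−r²)
- ratio, adjusted to change: 2(1−r)(1+r) / [4(1−r)] = (1+r)/2

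Exact generalised least squares on a layout of 3 arms by 4 visits, with s²=1, gives the same variances:

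| r (assumed) | Change | Adjusted | Ratio | Reduction |
|---|---|---|---|---|
| 0 | 4.00 | 2.00 | 0.50 | 50% |
| 0.3 | 2.80 | 1.82 | 0.65 | 35% |
| 0.5 | 2.00 | 1.50 | 0.75 | 25% |
| 0.8 | 0.80 | 0.72 | 0.90 | 10% |

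Estimating the baseline slope costs little. Simulating 36 people in six balanced sequences (an assumed layout) gave ratios of about 0.51, 0.66, 0.77 and 0.92.

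**Sensitivity to equal variances.** With k the ratio of follow-up SD to baseline SD, the variance ratio is k²(1−r²)/(1+k²−2rk). At k=1.2 it is 0.59 at r=0 and 0.997 at r=0.8. At k=0.8 it is 0.39 at r=0 and 0.64 at r=0.8.

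**Power with the plan's figures.** Assume that 0.07 is the SD of change in one arm and that changes are independent across arms. The SD of the between-arm difference in changes is then 0.07 × √2 = 0.099, and after adjustment 0.099 × √((1+r)/2). The test is a paired t with 36 people, two-sided alpha 0.05/3 (assuming three pairwise arm comparisons at one time point) and a difference of 0.06 m/s:

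| Analysis | SD (m/s) | Power |
|---|---|---|
| Change | 0.099 | 86% |
| Adjusted, r=0.8 | 0.094 | 90% |
| Adjusted, r=0.5 | 0.086 | 95% |
| Adjusted, r=0.3 | 0.080 | 97% |
| Adjusted, r=0 | 0.070 | 99% |

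At unadjusted two-sided 0.05 the change analysis already has about 94%. If 0.07 is instead the SD of the between-arm difference in changes, power on changes at alpha 0.05/3 is 99.4%, and the benefit is only in narrower intervals.

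**The other reading.** If the plan means arm differences at each visit, no baseline error enters and the variance is 2s². Adjustment then multiplies it by 1−r²: 1.00, 0.91, 0.75 and 0.36 at r = 0, 0.3, 0.5 and 0.8.

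**A common-baseline model with only a participant intercept.** Constraining the baseline means to be equal while keeping participant as the sole random effect reduces to a follow-up-only contrast, with variance 2.00 at every r. Against changes that is a ratio of 0.50 at r=0, 1.00 at r=0.5 and 2.00/0.80 = 2.5 at r=0.8.

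**The case against.** The strongest case on the other side has four parts.

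- **The criticised contrast is partly inferred.** No arm-by-time interaction is written, and a literal main-effects model yields no between-arm contrast of changes at all. This stands. The concern rests on the stated aim of comparing changes between arms. Under the visit-difference reading, adjustment still gains whenever r>0.
- **The size is unknown.** A reader might infer that half the information is being thrown away, because the plan's participant-only random effect implies r=0. The documents do not support that: a short model description is not evidence about the data. Visits within a period lie close together while periods are separated by a 4-week washout, so a positive r is plausible. Half is the best case.
- **Power may already be adequate.** A reader might infer that the trial is underpowered as planned. On the plan's own effect and SD it is not, under the assumptions in the working, and n=10 reproduces.
- **Change scores are defensible.** The endpoints are defined as changes, and with no period or carryover term in the model, subtracting each period's baseline gives some protection against drift and effects that outlast the washout. This stands as a reason to keep the change analysis, though not as the main one.

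**Conclusion.** The point holds as a worthwhile, inexpensive improvement in efficiency. With equal variances and r between 0 and 0.8, adjustment removes 50% to 10% of the variance of the between-arm contrast. In interval width that is a factor of √0.50 = 0.71 to √0.90 = 0.95. On the plan's 10-metre walk figures, power at alpha 0.05/3 goes from about 86% to between 90% and 99%, if 0.07 m/s is a one-arm SD and changes are independent across arms. The gain shrinks towards nothing as r approaches 1, or if follow-up is more variable than baseline and r is high.

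A reader might also infer that the planned comparison is biased or invalid. It is not: a difference of change scores is a legitimate estimate that is less precise than it need be.

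**What to change.** In the Statistical Analysis Plan section, replace the model description along these lines:

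- Responses: INT5, POST and 1WK.
- Fixed effects: arm, time, arm-by-time and period.
- Covariates: the period-specific baseline and the participant's mean baseline over the three periods.
- Random effects: participant and participant-by-period.
- Sensitivity analysis, prespecified: the unconstrained change-from-baseline comparison.

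Keeping baseline as a response with a common mean across arms is an acceptable alternative only with the participant-by-period effect included. With a participant intercept alone it can be less precise than change scores.

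The cost is wording: no extra visits, participants or procedures. There are two downsides. The adjusted estimate is somewhat biased if carryover past the 4-week washout differs by arm, which is why the change analysis is retained. And once baseline is a covariate, a period with a missing baseline drops out unless the plan says how it is handled, so a sentence on that is needed. Fixing the choice before analysis also prevents a later selection between the two results.

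### The mixed model names only time and arm as fixed effects; without an arm-by-time term it cannot give the changes within and between arms that the SAP promises

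*Combined protocol and SAP*

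**What the plan says.** The Statistical Analysis Plan section gives two targets for all functional gait outcomes. The model is to "jointly assess changes at INT5, POST and 1WK relative to baseline within each arm", and "as well as assess the changes between arms for each time point". With three arms and three follow-up times, that is nine within-arm changes and the differences between them.

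The next sentence gives the model: "The model will include time points (BL, INT5, POST, and 1WK as a categorical variable) and treatment arm". Time is a four-level factor with baseline (BL) as one of its levels. The other factor is "treatment arm (AIH + tSCS, SHAM AIH + tSCS, and SHAM + SHAM as categorical variable) as fixed effects", and the random part is subject alone. No arm-by-time term appears in this section or anywhere else in the document. Because BL is a level of the time factor, the outcome is the raw measurement and not a change score. No baseline covariate is named either.

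The design is a crossover: "All participants will complete three arms of the study" (Procedures Involved). Study Timelines places a separate baseline visit before each arm.

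**The concern.** A difference between arms in change from baseline is, by definition, an arm-by-time interaction. A model with time and arm as main effects assumes that this interaction is zero. The promised quantities are therefore fixed by the model and not estimated from the data.

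The software would still print a time effect and an arm effect, both with p-values, so the problem could pass unnoticed. The time effect would credit the double-sham arm with the average gain of all three arms. The arm effect would mix post-treatment differences with the pre-treatment visit. This is the only model given for the functional gait outcomes, which include the primary endpoint, the 6-minute walk test.

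**Working it through.** **The plan's own figure.** Sample Size and Power Considerations gives a difference of 0.06 m/s, an SD of change of 0.07 m/s, a one-sided paired t-test, alpha 0.05 and n = 10. The effect size is 0.06 / 0.07 = 0.857. Exact noncentral-t power is 0.8035 at n = 10 and 0.7583 at n = 9, so n = 10 reproduces. It rests on a t-test of changes, and the point below does not depend on it.

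**The model as listed.** For arm a and time t, the mean is E[Y(a,t)] = mu + alpha(a) + tau(t).

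- Fixed-effect parameters: 1 + (4 − 1) + (3 − 1) = 6, for 3 × 4 = 12 arm-by-time means.
- Change from baseline in arm a: tau(t) − tau(BL). The arm term cancels, so there are three distinct changes instead of nine.
- Difference in change between arms a and b: [tau(t) − tau(BL)] − [tau(t) − tau(BL)] = 0 at INT5, POST and 1WK. A check of the design matrix gave a zero contrast vector at all three.
- Arm difference: alpha(a) − alpha(b), one constant at every visit, BL included.

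**With arm-by-time added.** The interaction adds (3 − 1) × (4 − 1) = 6 parameters. The rank rises from 6 to 12, equal to the number of means, and all nine changes and their differences become estimable.

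**What the arm coefficient estimates.** With balanced data over T visits it is the average arm difference across those visits. If the difference is 0 at BL and delta at every later visit, it equals (T − 1)/T × delta:

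- T = 4 (BL, INT5, POST, 1WK): 0.75 delta.
- T = 3 (BL, POST and 1WK, the assessment visits in Study Timelines): 0.67 delta.
- T = 4 with an effect at 1WK only: 0.25 delta.

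These fractions have no units, so they apply to the 6-minute walk as well.

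**Worked example (assumed true values).** Take changes of 0.06, 0.03 and 0.00 m/s for AIH + tSCS, SHAM AIH + tSCS and SHAM + SHAM, constant after baseline.

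| Quantity | Truth | Time + arm | Time × arm |
|---|---|---|---|
| Change at 1WK, AIH + tSCS | 0.06 | 0.03 | 0.06 |
| Change at 1WK, SHAM AIH + tSCS | 0.03 | 0.03 | 0.03 |
| Change at 1WK, SHAM + SHAM | 0.00 | 0.03 | 0.00 |
| AIH + tSCS minus SHAM + SHAM | 0.06 | 0.045 (arm coefficient) | 0.06 |

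Here (0.06 + 0.03 + 0.00)/3 = 0.03, and (0 + 0.06 + 0.06 + 0.06)/4 = 0.045.

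**Simulation.** This used 100 data sets of 36 participants, an assumed between-subject SD of 0.25 m/s and an assumed residual SD of 0.07/√2 m/s, so that the SD of a change is 0.07. The additive model averaged a 1WK change of 0.030 for every arm and an arm coefficient of 0.046. The interaction model averaged 0.062 for AIH + tSCS, 0.001 for SHAM + SHAM and 0.062 for their difference. The pooled 1WK change had an unadjusted p below 0.05 in all 100 data sets, although the true change in the sham arm was zero.

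**The case against.** The strongest reply is that the stated aims imply the interaction. The section asks for changes "within each arm as well as assess the changes between arms for each time point", which an additive model cannot supply, and it never says that the two factors enter as main effects only. An analyst working from the aims would fit arm-by-time. Nor does the SAP name the arm coefficient as the treatment effect, so the dilution figures describe one possible misuse. This may well be a drafting omission. But the listed terms are the specification, and an analyst who adds a term to meet the aims is choosing the model outside the plan.

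Three further points limit the consequences, and they stand.

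- **Detection.** With randomised order and no arm effect, the additive arm coefficient has expectation zero. It can also be the more sensitive test. With 36 participants and the residual SD above (0.0495), its SE is 0.0495 × √(2/144) = 0.0058, against 0.0495 × √(4/36) = 0.0165 for the single-visit interaction contrast. For a constant effect of 0.06 the ratios are 0.045/0.0058, about 7.7, and 0.06/0.0165 = 3.6. For an effect at 1WK only, the order reverses: 0.015/0.0058 = 2.6 against 3.6. These SEs ignore any subject-by-period variance. The harm is to what is estimated; a general loss of power is not shown.
- **Baseline imbalance.** Each participant takes every arm, so with complete data stable differences between people cancel. What reaches the arm coefficient through baseline is visit noise, period effects and any carryover.
- **Scale.** The m/s values are for the 10-metre walk, a secondary endpoint, and the three-arm pattern is assumed. Only the fractions carry over to the primary endpoint.

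**Conclusion.** The concern holds: the model is wrong as written. With the listed terms, the between-arm difference in change is identically zero and each visit has one change common to all arms. That follows from the form of the model and needs no assumed values. The fractions 0.75, 0.67 and 0.25 assume balanced data, a literal additive fit, and an effect that is either constant after baseline or confined to the last of four visits. The m/s figures are illustrations. The aims point to the right model, but the specification contradicts them on the main analysis, and the comparisons to be Bonferroni-corrected are left undefined. It must be fixed before the analysis is run.

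**What to change.** Add the arm-by-time interaction to the fixed effects. Define the treatment effect as the change from BL to a named visit in AIH + tSCS minus the same change in the comparator arm. State this contrast for 1WK and for POST, list the comparators, and say which contrasts the Bonferroni correction covers. Report the within-arm changes from the same model. Study Endpoints does not say which visit is primary for the 6-minute walk, so the sponsor should name it in the same edit.

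The cost is about one sentence of SAP text and six more fixed-effect parameters with four time points, or (3 − 1) × (3 − 1) = 4 with three. No new data and no change to trial conduct are needed. The interaction does not by itself complete a three-period crossover model: the section also lists no period term and no subject-by-period random effect, and both should be considered in the same revision.
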